device was activated monthly to transiently disrupt the BBB before intravenous (IV) Carboplatin chemotherapy (Area under the Curve 5 dosing). Nineteen patients received at least one sonication. In 65 US sessions, BBB disruption was visible on T1w MRI for 52 sonifications. Treatment-related adverse events observed were transient and manageable: a transient edema at H1 and at D15. No Carboplatin-related neurotoxicity was observed. Patients with no or poor BBB disruption visible on MRI had a median Progression-Free Survival (PFS) of 2.73 months, and a median OS of 8.64 months. Patients with clear BBB disruption had a median PFS of 4.11 months and a median OS of 12.94 months.

A research group in Sunnybrook Research Institute follows another approach, where the generation of FUS is achieved through a 1024-element Insightec® ultrasonic array embedded within an MRI magnet. The multi-element hemi-spherical transducer called “ExAblate Neuro” has been approved by the FDA for MR-guided non-invasive thalamotomy for treatment of essential tremor [41]. Transcranial FUS application is possible through the electronic steering of the ultrasound beam and allows the capability of MR guidance. The first study showing safe, efficient, localized, reversible, and repeatable BBB opening in 5 AD patients using the ExAblate system was recently published [23]. AD patients received FUS treatments aimed at the dorsolateral prefrontal cortex. The size of the targeted area was 9×9 mm², achieved through a 3×3 grid multiple sonication design. BBB opening was fully reversible, with no contrast enhancement detected 1 day after treatment. Furthermore, there was no clinically significant worsening in the cognitive scores and no detectable reduction in beta-amyloid levels measured by ¹⁸F-PET post-sonication.

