10.1 Sample Size Determination

A minimum of 3 and maximum of 15 patients will be recruited in the study. The minimum number of subjects is to account for “dose” limiting toxicities disallowing more subjects to be enrolled. As this is a feasibility study, the power and sample size is not justified. However, successful methodology will be concluded if the BBB opening is safely opened in at least 75% of the cases as evidenced on MRI. The scan with the BBB opening will be compared to the scan before BBB opening for each patient. Power analysis shows that for a detectable difference of 72 mm^3 (after BBB opening - before BBB opening) and a standard deviation of 50 mm^3 , at least 6 subjects are needed to report a result at the level of $\alpha=0.05$ and Power=0.80 with paired student's t-test.

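### The 80% power at 6 subjects assumes that every subject contributes an opened scan (or that 72/50 already average in non-openers), and Section 10.1 does not say so

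*Combined protocol and SAP*

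**What the plan says.** Section 10.1 of the combined protocol and SAP gives the sizing effect as "for a detectable difference of 72 mm^3 (after BBB opening - before BBB opening" with "a standard deviation of 50 mm^3", and concludes that "at least 6 subjects are needed to report a result at the level of $\alpha=0.05$ and Power=0.80 with paired student's t-test". It describes the comparison, per patient, as the scan showing the opening against the scan before it.

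The same paragraph sets the feasibility criterion: "successful methodology will be concluded if the BBB opening is safely opened in at least 75% of the cases as evidenced on MRI". It does not define a case as a patient, a session or a site. It does not say whether 72 and 50 describe all treated subjects or only those whose barrier opened, or whether a subject without opening enters the comparison. It also says that the sample size is not justified by power, and gives a range of 3 to 15 subjects.

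Section 10.2 calls the analysis descriptive and names the Wilcoxon signed-rank test, not the t-test, for the before/after comparison. Section 7.6.1 defines opening by enhancement within 5 mm of the sonicated site. Section 12.6 foresees failure to open in 3 subjects as a trigger for contacting the regulator.

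**The concern.** Read literally, the 72 mm³ belongs to a subject whose barrier opened. The plan's success criterion allows up to a quarter of cases not to open, and Section 12.6 provides for subjects in whom opening fails. A non-opener kept in the comparison adds a change near zero, which lowers the mean and spreads the differences. A non-opener left out reduces the number of pairs below 6. Either way the stated power does not follow for 6 treated subjects unless all of them open.

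Two things are at stake. The 80% is the only power figure given for the imaging comparison, and readers may take it as applying to any 6 treated subjects. And leaving the handling of non-openers open allows them to be set aside after the scans are read. Because opening is itself defined by enhancement, restricting the comparison to opened scans selects on the outcome being tested.

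**Working it through.** **Inputs.** From Section 10.1: difference 72 mm³, SD 50 mm³ (read as the SD of the paired difference), alpha 0.05, n = 6, opening floor 75%. Two-sided testing is assumed because it is the version that gives 6. Further assumptions, not in the documents: a case is a patient, openers' changes are Normal(72, 50), and non-openers' changes have mean 0 and SD between 0 and 50.

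**Step 1: the plan's figure.** Paired t-test, df = n − 1, noncentrality (72/50)·√n = 1.44·√n. Power is 0.299 at n = 3, 0.503 at 4, 0.677 at 5 and 0.803 at 6. Six is the smallest n reaching 0.80, so the plan's figure is reproduced, with little slack. One-sided testing would already give 0.837 at n = 5.

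**Step 2: six treated, non-openers kept, t-test.** Each subject opens with probability p (simulation, 400,000 to 500,000 trials).

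| Opening rate | Power at n = 6 (non-opener SD 50 to SD 0) |
|---|---|
| 100% | 0.80 |
| 90% | 0.65–0.68 |
| 80% | 0.51–0.54 |
| 75% | 0.45–0.46 |

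**Step 3: six treated, non-openers dropped, t-test.** At 75% the number of openers k is Binomial(6, 0.75). Weight the Step 1 power at each k, with 0.128 at k = 2 and no test possible below that:

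0.178×0.803 + 0.356×0.677 + 0.297×0.503 + 0.132×0.299 + 0.033×0.128 ≈ 0.58.

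All six open with probability 0.75⁶ = 0.178.

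**Step 4: the planned Wilcoxon test.** With 6 pairs the exact two-sided test rejects at 0.05 only when all six changes have the same sign (attained level 2/2⁶ = 0.031). So power is essentially P(change > 0)⁶.

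- All open: Φ(1.44) = 0.925, and 0.925⁶ ≈ 0.63.
- 90% opening: 0.9×0.925 + 0.1×0.5 = 0.883, and 0.883⁶ ≈ 0.47.
- 75% opening: 0.75×0.925 + 0.25×0.5 = 0.819, and 0.819⁶ ≈ 0.30.

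These treat a non-opener's change as small noise, equally likely to be positive or negative. If a non-opener is dropped, or changes by exactly zero and is discarded, 5 pairs remain. The smallest attainable p-value is then 2/2⁵ = 0.0625, and the test cannot reach 0.05.

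**Step 5: the maximum of 15.** At 75% opening with non-openers kept, t-test power is 0.90–0.98 and Wilcoxon power about 0.89–0.95.

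**The case against.** The strongest reply is that nothing has been miscalculated: 72, 50 and 6 give 0.803. That stands. The issue is an unstated condition, not an arithmetic error.

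Second, a reader might infer that the power at 6 simply is 0.46. The documents do not support that. The 75% is a floor for declaring success, not an expected rate. A case may be a session: Section 7.5 schedules an opening MRI in every cycle, so a subject who fails to open once could still supply an opened scan later, and dilution per subject could be much smaller. If 72/50 already average over all treated subjects, non-openers included, the stated 0.80 applies. If the 6 means six opened pairs, it also applies.

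Third, the series cited in Section 2.3 ("In 65 US sessions, BBB disruption was visible on T1w MRI for 52 sonifications", or 80%) might be read as a per-patient rate for this trial. It counts sessions, in 19 patients, with an implanted device, so it shows only that non-opening happens.

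Fourth, the plan disclaims a power justification, calls the analysis descriptive, treats 6 as a lower bound and allows 15 subjects. This stands and limits the impact. It does not settle what the 80% refers to or which subjects are analysed.

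**Conclusion.** The point holds as a conditional one. The stated 0.80 at 6 subjects requires either that all 6 contribute an opened scan or that 72/50 already describe every treated subject, and Section 10.1 states neither. If 72/50 describe opened subjects, a case is a patient and the true rate is 75%, t-test power with 6 treated subjects is roughly 0.45 to 0.58, depending on whether non-openers are kept or dropped. The planned Wilcoxon test gives about 0.63 at n = 6 even if all open, and about 0.30 at 75% with non-openers kept.

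A reader might go further and conclude that the trial is too small. That does not follow: at the permitted maximum of 15 the power is high even at 75% opening, and the sample size does not rest on this calculation. What needs correcting is the unconditional wording and the missing rule for subjects who do not open.

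**What to change.** In Section 10.1, state that 80% power at 6 is conditional on opening in all 6. Alternatively, if it is so, state that 72 and 50 are the mean and SD over all treated subjects, non-openers included. Add power over a range of opening rates as a sensitivity figure, name the test, and compute it for the Wilcoxon test planned in Section 10.2. Under the model above that is about 0.63 at n = 6 if all open, 0.47 at 90% and 0.30 at 75%. Say whether a case is a patient, a session or a site.

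In Sections 10.1 and 10.2, state that all sonicated subjects with a post-sonication scan enter the before/after comparison whether or not opening was seen.

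Cost: text in both sections, including a definition of who is analysed. The stated power becomes less favourable and the estimated mean change may be smaller. No subjects are needed beyond the stated maximum of 15.

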6.2 Secondary Objective

- To evaluate the 6-month Progression Free Survival (PFS6) and 6-month Overall Survival (OS6)
- To determine blood brain barrier/tumor imaging changes using FUS in children with progressive DMG

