10. MEASUREMENT OF EFFECT

The MRIs should include volumetric sag T1 pre- and post- contrast images with reconstructions as well as dynamic contrast enhanced images (which will be acquired over a 30 minute period to allow for sufficient time for the contrast to cross the blood brain barrier site which was opened with FUS), axial post contrast SE T1 as well as sag T2 volumetric (with coronal and axial reconstructions) (can be acquired post-contrast), axial T2 FSE (can be acquired post-contrast), axial SWAN, axial FLAIR (must be acquired pre-contrast), and axial DWI (must be acquired pre-contrast). Initially, we will ideally choose the area for opening of the blood brain barrier with NgFUS at a peripheral site of the tumor, which does not demonstrate post contrast enhancement on the pre-treatment MRI. We will choose one site for blood brain barrier opening. We can measure contrast enhancement as described in Mainprize et al as well as has previously been measured by members of our group in past work (by investigators [name] and [name]). Radiological evidence of successful BBB opening and closing will also be noted as mentioned in [section 7.6.](#)

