10.2 Statistical Data Analysis

The data analysis will be descriptive. The continuous scan measures will be summarized by median, minimum and maximum. The categorical measures will be summarized by frequency and proportions, such as adverse events. Nonparametric Wilcoxon signed-rank test will be used to compare the gadolinium enhancement in the patient's brain before and after BBB opening.

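### The stated 80% power at 6 subjects belongs to a paired t-test, but the analysis section names a Wilcoxon signed-rank test, whose power at 6 is about 0.63 if exact and two-sided with normal differences

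*Combined protocol and SAP*

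**What the plan says.** Section 10.1 sets the enrolment range: "A minimum of 3 and maximum of 15 patients will be recruited in the study". It disclaims a formal basis for that range: "As this is a feasibility study, the power and sample size is not justified". It then gives a success rule: "successful methodology will be concluded if the BBB opening is safely opened in at least 75% of the cases as evidenced on MRI". It also gives a power statement for the within-patient comparison of scans before and after opening. For a difference of 72 mm³ and a standard deviation of 50 mm³, at least 6 subjects are said to be needed at alpha 0.05, with "Power=0.80 with paired student's t-test".

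Section 10.2 opens with "The data analysis will be descriptive", but then names a hypothesis test: "Nonparametric Wilcoxon signed-rank test will be used to compare the gadolinium enhancement in the patient's brain before and after BBB opening". It mentions no t-test, and no power for the Wilcoxon test appears anywhere. Sidedness is not stated for either test, and 10.2 does not say whether the Wilcoxon p-value is exact or approximate.

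The comparison serves a secondary objective in Section 6.2: "To determine blood brain barrier/tumor imaging changes using FUS in children with progressive DMG".

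**The concern.** A reader of 10.1 would conclude that six children give 80% power for the planned imaging comparison. That figure was worked out for a test the analysis section does not name. At very small n the difference matters, because a signed-rank test has only a few attainable p-values. At n = 6 the exact two-sided test can reject in one configuration only, and below 6 in none. Enrolment may end with as few as 3 subjects if toxicity intervenes, so these sizes are ones the protocol itself foresees.

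What is at stake is the stated power and the reading of the imaging comparison, not the primary conclusion. Suppose 6 subjects are treated and 5 show opening: 5/6 = 83%, which meets the 75% criterion if cases means subjects. Section 10 prefers a target site "which does not demonstrate post contrast enhancement on the pre-treatment MRI", so the sixth subject could show zero change. Five non-zero differences would remain, and the exact two-sided p could not fall below 0.0625. A met success criterion would then sit beside a non-significant test purely because of the count.

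**Working it through.** **Inputs.** From Section 10.1: mean difference 72 mm³, SD 50 mm³, alpha 0.05, target power 0.80, n = 6, enrolment 3 to 15. From Section 10.2: Wilcoxon signed-rank test.

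**Assumptions, because the protocol is silent.** The enhancement measure of 10.2 is the mm³ volume of 10.1. The 50 mm³ is the SD of the paired differences; if it were the SD of a single scan, the figure of 6 would hold only at a within-patient correlation of 0.5. The differences are normal.

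**Step 1: reproduce the plan's figure.** Effect size d = 72/50 = 1.44. For n = 6, df = 5 and the noncentrality is 1.44 × √6 = 3.527. Two-sided paired-t power is 0.803; at n = 5 it is 0.677. So 6 is the smallest n reaching 0.80, as stated. A one-sided t-test gives 0.837 at n = 5 and would have led to 5 subjects, so the plan's own figure implies a two-sided test.

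**Step 2: attainable p-values of the exact signed-rank test.** There are 2ⁿ equally likely sign patterns under the null, so the smallest two-sided p is 2/2ⁿ.

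| n | smallest two-sided p | smallest one-sided p |
|---|---|---|
| 3 | 0.25 | 0.125 |
| 4 | 0.125 | 0.0625 |
| 5 | 0.0625 | 0.031 |
| 6 | 0.031 | 0.016 (1/64) |

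Two-sided at 0.05, n = 3 to 5 can never reject. One-sided, only n = 3 and 4 cannot. At n = 6 the next two-sided value after 2/64 = 0.031 is 4/64 = 0.0625, so rejection requires all six differences to share a sign.

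**Step 3: power at n = 6.** P(difference > 0) = Φ(1.44) = 0.9251. Power = 0.9251⁶ + (1 − 0.9251)⁶ = 0.627; the second term is negligible. Simulation agrees (0.626 to 0.627).

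**Step 4: other sample sizes, both tests two-sided.**

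| n | paired t | exact Wilcoxon |
|---|---|---|
| 5 | 0.68 | 0 |
| 6 | 0.80 | 0.63 |
| 7 | 0.88 | 0.855 |
| 8 | 0.93 | 0.90 |
| 15 | 0.999 | 0.999 |

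At n = 7 the exact test rejects when the smaller rank sum is at most 2 (size 0.047).

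**Step 5: other readings of 10.2 at n = 6.**

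- Exact one-sided: power 0.89, size 0.047.
- Two-sided normal approximation with continuity correction: 0.63, because it too rejects only when all signs agree.
- Two-sided normal approximation without correction: 0.82. It also rejects at a rank sum of 1 (p = 0.046), so its true size is 4/64 = 0.0625, above the stated alpha.

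**Step 6: sensitivity to the distribution of differences.** Exact two-sided power at n = 6 depends only on the chance q that a subject's difference is positive. It is essentially q⁶: 0.53 for q = 0.90, 0.63 for 0.925, 0.89 for 0.98, and 1.00 for q = 1.

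**Step 7: the zero-change example.** One zero among six leaves 2⁵ = 32 sign patterns. The smallest two-sided p is 2/32 = 0.0625, whether the zero is dropped or handled by Pratt's method.

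**The case against.** The strongest reply is that nothing in the plan turns on this number. The sample size is declared unjustified, the analysis descriptive, imaging change secondary, and success a proportion. Six is a floor rather than the planned size: at 9, one of the two target totals considered in Section 12.3, exact two-sided power is 0.94. That stands, and it is why the effect is limited. It does not make the two sections agree: the protocol chose to print a power figure and to name a test, and they do not match.

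Second, 10.1 works in mm³ and 10.2 speaks of gadolinium enhancement. If the latter is a percentage or signal change, the ratio 72/50 does not apply and neither does 0.63. That too stands as a condition. But 10.1 would then carry no power statement for the comparison in 10.2, so the gap would remain in another form.

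Third, exactness is assumed. The uncorrected normal approximation gives 0.82 at n = 6 and p = 0.043 at n = 5 with all signs equal, so the impossibility below 6 depends on the version used. True, but at n = 5 and n = 6 that version has a real size of 0.0625, while the corrected version gives the same 0.63 at n = 6. Two-sidedness is less open to dispute, because 10.1's own figure implies it.

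Fourth, the worked example needs an exact zero on a continuous measure, and the non-enhancing site is only the ideal choice. A small positive sixth change would give p = 0.031. The example shows what can happen, not what is expected.

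Finally, planning with a t-test and analysing with a rank test is not a logical contradiction, and a rank test is defensible at this size. Agreed, but the stated power must then be that of the rank test.

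**Conclusion.** The concern holds. The t-test calculation is correct, but its power is attached to a test that Section 10.2 does not name. With the mm³ measure common to both sections, normal differences with SD 50 mm³, and an exact two-sided test at 0.05, power at 6 subjects is 0.63 rather than 0.80, and no result is significant at 3 to 5. Across the other versions of the test, the figure at 6 runs from 0.63 to 0.89. The shortfall is confined to very small n and is gone at 7. The primary conclusion is unaffected; the power statement and the interpretation of the secondary imaging comparison are. It should be fixed, though it is not critical.

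**What to change.** Name the same test, measure and sidedness in 10.1 and 10.2. Either of two edits does this.

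- **Option A.** In 10.2: *two-sided paired t-test at 0.05 on the change in enhancing volume (mm³), with the exact two-sided Wilcoxon signed-rank test as a sensitivity analysis*. Section 10.1 can then stay as it is. Preferring the t-test is partly a matter of taste, since normality cannot be checked at this size.
- **Option B.** Keep the Wilcoxon test in 10.2, stating that it is exact and two-sided at 0.05 on the change in mm³. Restate 10.1 as *at least 7 evaluable subjects (power about 0.855 for 72 mm³, SD 50 mm³, normal differences; 0.63 at 6)*. Add: *With fewer than 6 evaluable subjects (non-zero differences), the change is reported as median, minimum and maximum without a significance test.*

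The cost is one or two sentences in Section 10. No patients are added beyond the plan, since 7 lies within the existing maximum of 15.

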10.2 Statistical Data Analysis

The data analysis will be descriptive. The continuous scan measures will be summarized by median, minimum and maximum. The categorical measures will be summarized by frequency and proportions, such as adverse events. Nonparametric Wilcoxon signed-rank test will be used to compare the gadolinium enhancement in the patient's brain before and after BBB opening.

11. ADVERSE EVENT REPORTING

11.1 Definitions

Adverse Event

An adverse event (AE) is any untoward or unfavorable medical occurrence in a human subject, including abnormal sign, symptom or disease associated with the subject's participation in research, whether or not considered related to the subject's participation in the research. For the treatment period and 30 days post, all adverse events (AEs) according to the Common Terminology Criteria for Adverse Events (CTCAE) version 5.0 will be captured. Baseline abnormalities or pre-existing conditions will be identified and recorded as part of the pre-treatment work-up. Pre-existing conditions will not be subsequently reported as adverse events unless the severity increases after the start of treatment, or unless the pre-existing condition resolves and then recurs during treatment. After day 30 of follow-up, only grades 3, 4, and 5 AEs will be captured through 90 days following the neurosurgical procedure. All recorded AEs must have their attribution to the study procedures recorded, as well as their onset and resolution date (if known).

Serious Adverse Event

A serious adverse event (SAE) is any AE that is:

- fatal
- life-threatening
- requiring inpatient hospitalization/prolongation of existing hospitalization, unless:
 - routine treatment or monitoring of the studied indication, not associated with any deterioration in condition (procedures such as central line placements, paracentesis, pain control)
 - elective or pre-planned treatment for a pre-existing condition that is unrelated to the indication under study and has not worsened since the start of study the drug
 - social reasons and respite care in the absence of any deterioration in the subject's general condition
- resulting in persistent or significant disability or incapacity
- a congenital anomaly or birth defect
- an important medical event

Important medical events are those that may not be immediately life threatening but are clearly of major clinical significance. They may jeopardize the subject and may require intervention to prevent one of the other serious outcomes noted above.

Any adverse event that results in hospitalization or prolonged hospitalization should be documented and reported as a serious adverse event unless the AE meets one of the criteria listed below:

- Hospitalization or prolonged hospitalization for diagnostic or elective surgical procedures for a preexisting condition. Surgery should not be reported as an outcome of an adverse event if the purpose of the surgery was elective or diagnostic and the outcome was uneventful

- Hospitalization or prolonged hospitalization required to allow efficacy measurement for the study
- Hospitalization or prolonged hospitalization for therapy of the target disease of the study, unless it is a worsening or there is increase in the frequency of hospital admissions as judged by the clinical investigator
- Prolonged stay at MSCHONY at the Investigator's discretion unless it is for an adverse event that otherwise qualifies as an SAE

Unanticipated Problem

An unanticipated problem is any incident, experience or outcome involving risks to subjects or others in any human subject research that meets all of the following criteria:

- Unexpected (in terms of nature, severity or frequency) given (a) the research procedures that are described in the IRB-approval protocol and informed consent document, and (b) the characteristics of the subject population being studied;
- Related or possibly related to participation in such research (e.g., there is a reasonable possibility that the incident, experience or outcome may have been caused by the procedures involved in such research); and
- Suggests that the research places subjects or others at a greater risk of harm (including physical, psychological, economic or social harm) than was previously known or recognized.

All unanticipated problems meeting the criteria above will be reported to the IRB within 1 week of investigator/study staff awareness of the event (or other time frame required by the most current IRB reporting policies). Additionally, the sponsor-investigator will submit a summary of all unanticipated problems that occurred since the beginning of the study at the time of continuing review. Copies of each report and documentation of IRB notification and receipt will be kept in the Regulatory Binder.

Suspected Adverse Reaction (SAR)

In accordance with 21 CFR 312.32(a), a suspected adverse reaction (SAR) means any adverse event for which there is a reasonable possibility that the drug caused the adverse event.

Unanticipated Adverse Device Effect (UADE)

An unanticipated adverse device effect (UADE) is any serious adverse effect on health or safety or any life-threatening problem or death caused by, or associated with, a device, if that effect, problem, or death was not previously identified in nature, severity, or degree of incidence in the investigational plan or IDE application (including a supplementary plan or application), or any other unanticipated serious problem associated with a device that relates to the rights, safety, or welfare of subjects.

Associated with the investigational device: There is a reasonable possibility that the adverse effect may have been caused by the investigational device.

